9.5 Study size

The sample size considerations are based on the expected VTE incidence for COC_{LNG}.

. It is expected that NOMAC-E2 is associated with a VTE risk that is not higher than the risk associated with COC_{LNG}.

The study should be powered to test non-inferiority of NOMAC-E2 treatment regarding VTE risk in comparison to COC_{LNG} use. Sample size calculations for a non-inferiority test of two exponential survival curves [4;5] showed that an expected number of 150 VTE cases should be sufficient to reach this goal. These calculations are based on the following assumptions: 1) one-sided α of 0.05; 2) power (1- β) of 0.80 and 3) non-inferiority limit on hazard ratio of 1.5.

At an incidence rate of 10.0/10,000 WY a total of 150 VTE cases could be expected within 150,000 WY. The drop-out rate in similar studies has been approximately 0.7% per month. Assuming 1) a recruitment phase of 36 months, 2) a follow-up phase of 12 - 24 months, and 3) a loss to follow-up rate of about 5%, follow-up of 101,000 study participants (50,500 NOMAC-E2 users and 50,500 COC_{LNG} users) for up to 24 months would result in approximately 150,000 WY (see table 1).

Based on these scenarios, the study is sufficiently powered to exclude a 1.5-fold VTE risk for NOMAC-E2 users compared to COC_{LNG} users in the event that the true VTE risk among NOMAC-E2 users is not higher than among COC_{LNG} users.

However, precise power calculations based on actual incidences and drop-out rates should be done on the basis of follow-up data 1) before the end of the recruitment phase and 2) after availability of 30,000 WY of observation. If these calculations do not confirm the assumed incidence and drop-out rates the Safety Monitoring and Advisory Council will discuss the need to decrease or increase the number of study participants and/or follow-up times.

²² 'idiopathic' pulmonary embolism and deep venous thrombosis of the lower extremities

PASS – Safety of nomegestrol/estradiol: Study Protocol Version 4.0 20 JUN 2019

The sample size needed for the investigation of the VTE risk is also sufficient for the evaluation of secondary outcomes – except ATE. Acute myocardial infarction and stroke are very rare in a female population of reproductive age. This study is powered to exclude a 2.5-fold risk of ATE. This is sufficient to screen for safety signals and substantial effects.

Table 1: Expected observation time

Assumptions: approx. 101,000 study participants recruited over 36 months (~ 2,806 per month); follow-up of study participants for 12 - 24 months; drop-out rate of 0.7% per month (e.g., 20 out of 2,806 recruited women will drop-out during the first month after recruitment; therefore the average number of women during the first month is 2,796 women [(2,806+2,786) x 0.5]); loss to follow-up and loss to 'within study switchers': 11%

		Sub-cohorts recruited during month						
Time after study	1	2		24	25		36	
start [month]	Average number of women in follow-up							
1	2,796							
2	2,776	2,796						
24	2,379	2,395		2,796				
25		2,379		2,776	2,796			
26				2,757	2,776			
36				2,588	2,606		2,796	
47				2,395	2,412		2,606	
48				2,379	2,395		2,588	
WY	5,164	5,164		5,164	4,965		2,691	
Total WY (crude)	170,023							
Total WY (corrected for loss to follow-up and 'within study switchers' who do not contribute to exposure of starter and restarter)				~151,000				

PASS – Safety of nomegestrol/estradiol: Study Protocol Version 4.0 20 JUN 2019

9.6 Data management

9.6.1 Databases

Two different databases are used for data collection; the administrative database (ADB) and the study database (SDB).

The ADB is provided by ZEG to the national field organizations. Physician details, as well as data from the study participant, can be entered and maintained in this database.

The SDB is validated according to GXP rules. It contains all questionnaire data including baseline data and all subsequent follow-ups. ZEG regularly performs cross-check and verification checks on the data and any inconsistencies or unanticipated answers are mailed to the field organizations for further clarification.

From the questionnaire data, event data is derived from the SDB. All disease diagnoses are coded using the ICD-10 (International Classification of Diseases). ZEG also uses additional codes for the coding of events that are of specific interest (e.g. VTE during pregnancy or delivery, outcome of an unintended pregnancy: induced or spontaneous abortion, delivery of a healthy child, birth defects).

Concomitant medication is coded using WHO ATC-Codes. Surgical procedures are coded using the modified operation and procedure coding list (OPS) provided by DIMDI (German Institute for Medical Documentation and Information). All other relevant information will be coded by a ZEG specific, highly standardized coding system (ZEG Coding Dictionary). All outcomes of interest are additionally described in a case narrative, the "case summary".

9.6.2 Dataflow

When questionnaires are received from study participants, all pages are counted and the questionnaire is date-stamped. Questionnaires are to be checked for correct subject identification number, missing pages, legibility, and incomplete information on the questionnaires. Missing pages, illegible or missing information are requested from the study participants prior to data entry of the respective questionnaire.

Data is entered by double data entry via formatted entry screens designed to reflect the appearance of the questionnaire. Discrepancies between first and second data entry are identified by comparison of the two entry files within the statistical software

PASS – Safety of nomegestrol/estradiol: Study Protocol Version 4.0 20 JUN 2019

SAS. The decision on the true entry is done by the responsible data manager at ZEG. This may require direct contact with the study participant who filled in the questionnaire. Corrections will be made to the questionnaire only after contact with the study participant or her treating physician. All corrections are dated and initialed by the data manager who received the relevant new information (e.g., via direct contact or by a copy of medical reports/documents). The incorrect entry will be crossed out; however, it must remain legible, and the correct entry will be placed next to it. The reason for any correction of medical data on the questionnaire must be documented.

Quality control of entered data will be supported by SAS plausibility programs which include range, coding, missing and date checks as well as cross-reference (consistency) checks between variables.

9.6.3 Database Freeze/Lock

For each interim analysis and for the final analysis the database is frozen at a predefined time point. The database will be 'cleaned' within 4 weeks of the database freeze. After the final freeze (approximately 4 months after the last follow-up questionnaires have been sent to the study participants), no additional incoming data is entered in the database – this database will represent the final data source for all analyses. Safety copies are made of each database, so that all calculations can be repeated if necessary.

9.7 Data analysis

Based on available data and pharmacological considerations the *a priori* assumption is that use of NOMAC-E2 is not associated with an increased risk of VTE compared to COC_{LNG}. That is, a statistical comparison of NOMAC-E2 and COC_{LNG} is not expected to show a difference. Therefore, the Principal Investigator and the Safety Monitoring and Advisory Council (cf. section 10.3) have chosen a non-inferiority design to investigate the VTE risk of NOMAC-E2. The primary analysis will be based on the comparison of the upper confidence limit for the point estimate of the VTE²³ hazard ratio with the predefined non-inferiority limit (see below).

²³ DVT of the lower extremities and pulmonary embolism, cf. Section 8

PASS – Safety of nomegestrol/estradiol: Study Protocol Version 4.0 20 JUN 2019

The final analyses will include both an "as treated" (AT) and an intention-to-treat (ITT) analysis using Cox regression models. The safety conclusions of the study, however, will be based on the AT analyses (outcomes of interest will be assigned to the treatment she used at the time of the event) because the ITT approach (outcomes of interest are assigned to the treatment which was prescribed at study entry) potentially dilutes differences between treatments.

Incidence rates, incidence rate ratios (HRs), excess risks, as well as crude and adjusted hazard ratios will be calculated. The appropriate confounding variables will be built into the model. Based on the expectation of a small absolute number of serious outcomes of interest the number of confounding variables will be limited to wellestablished risk factors for these outcomes (e.g., age, BMI, duration of current use, and VTE history). Different modeling approaches will be used for the final multivariable model. The primary analysis model will be an *a-priori* expert model that is content driven and includes well-established prognostic factors. Additional sensitivity analysis models will be constructed to capture the influence of selected confounding factors and possible bias due to missing data. The final decision on the confounding variables will be made by the Safety Monitoring and Advisory Council before the first interim analysis of follow-up data. In addition, alternative analysis will be performed with other potential baseline risks to check the appropriateness of this decision. Similar analyses will be performed for all VTE (cf. Section 8) and arterial thromboembolism (e.g., acute myocardial infarction and stroke), the other secondary variables and other serious adverse events.

The null hypothesis to be tested is: $HR_{VTE} \ge 1.5$ (i.e., the VTE hazard ratio for NOMAC-E2 vs. COC_{LNG} is higher than or equal to 1.5). The alternative hypothesis is: $HR_{VTE} < 1.5$.

In the case of VTE it is conceivable that the proportional hazard assumption that effect parameters multiply hazard does not hold. Therefore, time-dependent factors will be included in the Cox model. The appropriateness of the model will be checked by comparing results of this analysis with results of an alternative analysis which stratifies by time of exposure. This stratification addresses also the potential problem of effect modification by current duration of use.

Real-life field studies frequently face the situation of missing data. The multiple reasons include superficial reading of the questions, misunderstanding of the questionnaire or simply unwillingness to give certain information. The questionnaires of this study have a clear layout and most questions have been tested in several former studies in large populations. The amount of missing information will be minimized by contacting participating women several times. If the missing information

PASS – Safety of nomegestrol/estradiol: Study Protocol Version 4.0 20 JUN 2019

can also be collected by the enrolling physician (e.g. any information on prescription, details regarding pregnancies, etc.), he/she will be contacted. If these strategies are unsuccessful, missing variables will be either accepted or, for certain variables, e.g. BMI, the last value will be carried forward. In general, missing data will comprise less than 5% of all data collected. To assess a possible effect of missing data on the primary outcome value, the *a-priori* expert model will be accompanied by multiple imputation of missing data regarding predefined prognostic factors.

A detailed statistical analysis plan addressing descriptive and inferential statistics will be developed by the study team during the first year after study start. This plan will include methodological details (e.g., censorship at time of cancer diagnosis, surgery or occurrence of other acute VTE risk factors for the analysis of VTE), a specification of sub-analyses (such as stratification by dose of ethinylestradiol (e.g., HR_{VTE} for NOMAC-E2 vs. COC_{LNG} with 20mcg of ethinylestradiol) and current duration of use (e.g., HR_{VTE} during the first year of use)) as well as a comprehensive set of mock tables for the presentation of the study results. The final analysis plan will be approved by the Safety Monitoring and Advisory Council before the first interim analysis of follow-up data. Changes of this document are to be approved by the Safety Monitoring and Advisory Council.

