9.2.2 Selection of Study Population

Approximately 50,500 NOMAC-E2 users and 50,500 users of COC_{LNG} will be recruited by participating physicians, including adolescents. The proportion of adolescents is expected to be in the range between 10% and 15%. Overall, 101,000 study participants are needed in order to provide approximately 150,000 woman-years (WY) (cf. Section 9.5), assuming a drop-out rate of approximately 0.7% per month for both continents. Approximately 90% of subjects will be recruited in Europe and the other 10% in Australia. Subsequent to these original assumptions, the study was expanded to Latin American countries (Colombia and Mexico).

Recruitment of study participants will be conducted via existing networks of COCprescribing health care professionals (e.g. gynecologists and general practitioners) who have participated in similar cohort studies in the past. Physicians should recruit NOMAC-E2 and COC_{LNG} users in an approximate 1 to 1 ratio. It is expected that this ratio reflects approximately the ratio of starter and restarter prescriptions of NOMAC-E2 and COC_{LNG} under routine clinical conditions. For every NOMAC-E2 user recruited, the physician should recruit the next new COC_{LNG} user (starter or restarter) who is willing to participate in the study.

Subjects will be considered for enrollment in this study after the participating physician has determined that NOMAC-E2 or COC_{LNG} use is appropriate. There will be no specific medical inclusion/exclusion criteria and no age restrictions (to fulfill the pediatric investigation plan (PIP) requirement in the EU). However, women who 1) have been pregnant within 3 months before treatment initiation or 2) have a history of cancer/chemotherapy or an increased genetic risk for VTE at baseline will be excluded from the analysis of VTE. All women who are eligible are to be asked by their physician if they are willing to participate. As this is a non-interventional study, the possibility to participate in the study should not be discussed with the study participant before both

PASS – Safety of nomegestrol/estradiol: Study Protocol Version 4.0 20 JUN 2019

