The following information will be recorded at the baseline visit after the study participant has provided written informed consent: prescribed COC, user status (starter/restarter), demographic and medical history, including medication history, acne, history and duration of use of hormonal contraceptives, as well as the addresses, e-mail addresses and phone numbers of the study participant, relatives or friends, and the primary care physician. Names, addresses and phone numbers are to be documented on a separate sheet, in compliance with data protection regulations.

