In contrast, it will be impossible to exclude diagnostic bias. Clinical symptoms of VTE cover the spectrum from a complete absence or unspecific, slight symptoms to dramatic, acute, life-threatening symptoms [17;18;19]. A high awareness of potential cardiovascular risks of combined oral contraceptive use may lead to more diagnostic procedures and, therefore, to more detected VTE. It is conceivable that this potential bias lead to an overestimate of the relative risk of a new product (such as NOMAC-E2) cohorts compared to the LNG-cohort. Therefore, diagnostic bias should not result in an underestimate of the VTE risk carried by NOMAC-E2.

Unlike in many other observational studies on hormonal contraceptives, a strength of the study will be the availability of information on many important prognostic factors for the outcomes of interest. Nevertheless, we acknowledge that due to the non-interventional character of the study, information on specific gene mutations will only be available for VTE cases but not for the vast majority of study participants who will not experience a VTE. This limitation will be mitigated through information on family history of VTE which has a higher predictive value for VTE compared to gene mutations [20].

This study combines several methodological strengths that are substantial for the validity of the results: i) prospective, comparative cohort design; ii) availability of important confounder information (e.g., BMI and family history of VTE); iii) validation of outcomes of interest and the exposure of the relevant cases; iv) comprehensive follow-up procedure and very low loss to follow-up to minimize underreporting; v) independent, blinded adjudication of VTE cases; vi) relevant statistical analyses (e.g., stratified analyses by user status and exposure period; comparison of isochronous, new user cohorts; sensitivity analyses on the impact of the adjudication process, outcome definition, and prognostic factor/covariate selection); vii) study population representative for oral contraceptive users under routine clinical conditions; viii) generalisability of results as COC use in this study reflects routine clinical use and

PASS – Safety of nomegestrol/estradiol: Study Protocol Version 4.0 20 JUN 2019

study participation is not limited by medical inclusion and exclusion criteria; ix) supervision by an independent Safety Monitoring and Advisory Council, and scientific independence from the study funder.

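### Neither covariate list for the primary VTE hazard ratio includes starter/restarter status or country, and the two lists disagree with each other

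*Protocol*

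**What the plan says.** The Abstract (Variables) names four adjustment variables for the primary VTE hazard ratio: age, BMI, duration of current use and family history of VTE. That list is closed.

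Section 9.7 is open. Because few events are expected, "the number of confounding variables will be limited to wellestablished risk factors for these outcomes". The variables that follow are examples, and the fourth is VTE history, not family history. The primary model is to be an a-priori expert model. The SMAC settles the covariates before the first interim analysis of follow-up data, and alternative models with other baseline risks are to check its choice.

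User status is collected: Section 9.2.3 lists "prescribed COC, user status (starter/restarter), demographic and medical history, including medication history". In the analysis it appears only in Section 9.9, which mentions "stratified analyses by user status and exposure period" among the strengths of the study. No section adjusts or stratifies by country. Country is not a named baseline item, but it follows from participants' addresses (Section 9.2.3) and from the national field organisations (Section 9.6.1).

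Section 9.2.2 asks physicians to recruit "users in an approximate 1 to 1 ratio". The comparator for each NOMAC-E2 user is the next willing new user of a levonorgestrel COC, whether starter or restarter. The same section says that Colombia and Mexico were added after the original planning assumptions.

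**The concern.** This is a non-randomised comparison, so the primary hazard ratio is only as good as its adjustment set. Two design features that could differ between the cohorts are in neither list.

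**User status.** The cohorts are made up of first-ever users and of women restarting after a break of at least two months. The recruitment rule does not match on this. Duration of current use does not replace it: on the natural reading, both kinds of user begin a new episode at study entry, so both start at zero.

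**Country.** Twelve countries on three continents contribute. Pairing within a physician would hold country mix close between cohorts, but it is only approximate. Some features of the design could let recorded VTE rates vary by country. Loss-to-follow-up targets differ by region (below 10% in Australia, below 5% in Europe, none stated for Latin America; Section 9.2.6). An event can also count as confirmed without imaging (Section 9.10.1).

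**Timing.** If interim report 1, dated October 2015, carried the first interim analysis of follow-up data, the covariate choice was due before the 2019 amendments documented the Latin American expansion. Nothing in the protocol requires the choice to be revisited.

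At stake is the estimate that is compared with 1.5. The planned stratified and alternative analyses could reveal a problem but would not correct that estimate.

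**Working it through.** **1. The plan's own figure.** Inputs from Section 9.5: "one-sided α of 0.05", power "of 0.80 and 3) non-inferiority limit on hazard ratio of 1.5", and "an expected number of 150 VTE cases should be sufficient to reach this goal". With 1:1 cohorts and a true HR of 1, the Schoenfeld formula gives

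D = 4 × (1.645 + 0.842)² / (ln 1.5)² = 150.4.

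Rounded up, this is 151, and power at 150 events is 79.9%. The stated 150 reproduces, so the point is not about sample size.

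**2. Unequal cohort sizes are a minor issue.** With 150 events, power is 79.6% at 55:45 and 78.5% at 60:40. An approximate ratio costs little power in itself. What matters is whether the cohorts differ in composition.

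**3. The two covariate lists side by side.**

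| | Abstract | Section 9.7 |
|---|---|---|
| Type of list | closed | examples only |
| Fourth variable | family history of VTE | VTE history |
| Starter/restarter | absent | absent |
| Country or region | absent | absent |

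Family history and a woman's own history are different variables. Section 9.9 refers to family history. Section 9.2.2 does not exclude women with a previous VTE from the VTE analysis, so the difference matters.

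**4. Illustration of an unadjusted binary factor.** The protocol gives no starter shares, country shares or rate ratios, so pN, pL and RR below are assumptions. They are the shares with the factor among NOMAC-E2 and levonorgestrel users, and its VTE rate ratio. The factor is taken as independent of the covariates already in the model.

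- Bias factor on the HR: b = [1 + pN(RR − 1)] / [1 + pL(RR − 1)]
- SE of log HR: 2/√150 = 0.163
- Chance of declaring non-inferiority: Φ{[ln 1.5 − ln(HR × b)]/0.163 − 1.645}

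Worked case with pN 20%, pL 40%, RR 2: b = 1.2/1.4 = 0.857. At a true HR of 1.5 the chance is Φ(0.154/0.163 − 1.645) = Φ(−0.70) = 24.2%.

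| pN vs pL | RR | b | Non-inferiority declared, true HR 1.5 | Power, true HR 1 |
|---|---|---|---|---|
| no imbalance | any | 1 | 5.0% | 79.9% |
| 20% vs 30% | 1.25 | 0.977 | 6.7% | 83.7% |
| 20% vs 30% | 1.5 | 0.957 | 8.5% | 86.7% |
| 20% vs 30% | 2 | 0.923 | 12.4% | 90.8% |
| 20% vs 40% | 1.25 | 0.955 | 8.7% | 86.9% |
| 20% vs 40% | 1.5 | 0.917 | 13.3% | 91.5% |
| 20% vs 40% | 2 | 0.857 | 24.2% | 96.3% |
| 40% vs 20% | 1.25 | 1.048 | 2.7% | 71.0% |
| 40% vs 20% | 1.5 | 1.091 | 1.5% | 62.0% |
| 40% vs 20% | 2 | 1.167 | 0.5% | 45.8% |

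A factor commoner among levonorgestrel users lowers the HR by about 2-14%. The reverse imbalance raises it and costs power.

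**The case against.** The strongest reply is that Section 9.7 does not fix the model. Its list is illustrative, the SMAC decides, and a statistical analysis plan that is not available here may already include both variables. This stands in part: a reader might infer that the primary model is known to omit them, but only the Abstract's closed list supports that.

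Second, user status is not ignored. Stratified analyses are named in Section 9.9 and alternative models in Section 9.7. That is true, but those are secondary to the estimate tested against 1.5.

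Third, no passage says that starters and restarters differ in VTE risk at equal duration of use, or that diagnostic practice differs by country. That stands. Section 9.9 speaks only of raised risk in the first months of use. The case for adjustment is precaution in a non-randomised study, not a documented effect. First-ever users are probably younger, and age is in the model, so residual bias would be smaller than the table shows.

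A reader might also infer that softening the 1:1 wording unbalanced starters and restarters. The documents do not support this. The rule takes the next comparator user of either status, so it never balanced user status. At most it bears on physician and country mix. The amendment table presents the wording as a clarification made in June 2019, about three months before the planned end of recruitment.

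**Conclusion.** The point holds as one of specification. Neither stated list includes user status or country, the lists disagree on whether they are closed and on the fourth variable, and the covariate decision was tied to a milestone that probably preceded the documented expansion.

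The size and direction of any confounding cannot be derived from the protocol. The ranges of 2-14% on the HR and about 7-24% instead of 5% rest on assumed rate ratios of 1.25-2, assumed imbalances of 10-20 points and no overlap with the existing covariates. A reader might infer that the HR is biased in favour of NOMAC-E2 or that the error rate is in fact inflated. The documents show neither, and the reverse imbalance would work against NOMAC-E2. The uncertain direction is the reason to settle the model in advance.

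**What to change.** - Reconcile the Abstract with Section 9.7: one closed list for the primary model, stating whether family history of VTE, personal history of VTE or both are meant.
- Add starter/restarter status to the primary Cox model as a covariate or stratum.
- Stratify the baseline hazard by country, with small countries pooled into regions by a rule fixed before the final analysis.
- Keep the four-covariate model as a sensitivity analysis.

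The cost is one changed model specification, approved by the SMAC, with no new data collection. User status adds one coefficient and country stratification adds none, so the expected small number of events is no obstacle. The loss of precision is negligible if both products are used within most strata. For example, a 60:40 split within strata keeps 0.24/0.25 = 96% of the information of an even split. If the statistical analysis plan already specifies this, only the protocol text needs to be aligned.
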